1. INTRODUCTION

This statistical analysis plan (SAP) provides guidelines for the final presentation and analysis for the PROcalcitonin and NEWS2 evaluation for Timely identification of sepsis and Optimal use of antibiotics in the emergency department (PRONTO) trial. This plan, along with all other documents relating to the analysis of this trial, will be stored in the Statistical Analysis Master File electronically within the Trial Master File.

Any deviations from the SAP will be recorded and justified in the SAP deviation log (at the end of this document) and the final report. The analysis will be conducted by an appropriately qualified statistician, who will ensure data integrity by adhering to the guidelines set out in the CTR's (Centre for Trials Research) SOPs (Standard Operating Procedures). This SAP will be reviewed by the senior trial statistician (STS) and approved by the Trial Management Group (TMG) before being signed off by the author ([name]), STS ([name]), and the Chief Investigators ([name] and [name]). A copy of the SAP will be sent to the Trial Steering Committee (TSC) and Independent Data Monitoring Committee (IDMC) statisticians for review and amended as appropriate. This SAP includes the quantitative aspects of the analysis; health economics and qualitative analysis plans will be provided separately.

2. BACKGROUND

2.1 RATIONALE AND RESEARCH QUESTION

Full trial details are provided in the PRONTO trial protocol and the protocol paper (Euden et al., 2022).

Sepsis is a common, potentially life-threatening complication of infection. The optimal treatment for sepsis includes early recognition, prompt antibiotics and fluids into a vein (intravenous/IV). Currently, clinicians assess severity in patients in the Emergency Department (ED) with the National Early Warning Score (NEWS2). It is not specific and tends to over-diagnose sepsis leading to over-prescribing of antibiotics and promoting antimicrobial resistance. Adults with suspected sepsis fall into one of three categories: a) those looking ill needing urgent IV antibiotics and fluids within 1 hour, b) those who are unwell, but will not come to harm if IV antibiotics within 3 hours, c) those not critically unwell who may or may not need IV antibiotics. Procalcitonin (PCT), a blood test not widely used in the NHS, helps to identify bacterial infection. The National Institute for Health and Care Excellence (NICE) recommended further research on PCT testing in EDs for guiding antibiotic use in people with suspected sepsis.

2.2 OBJECTIVES

TPL/008/2(v1.0)

Canolfan Ymchwil Treialon

Short title:	ISAP / SAP Template

Primary objective: To determine whether the addition of PCT measurement to NEWS2 scoring can lead to a reduction in IV antibiotic initiation in ED patients managed as suspected sepsis, with at least no increase in 28-day mortality compared to NEWS2 scoring alone (in conjunction with local standard care pathways).

Secondary objectives: To determine if the use of PCT and NEWS2 in the assessment of suspected sepsis is:

- i. cost-effective
- ii. feasible
- iii. acceptable to patients and their families

3. STUDY MATERIALS

3.1 TRIAL DESIGN

Parallel, two-arm, open-label, individually randomised controlled trial with two co-primary endpoints, an internal pilot phase, and group-sequential stopping rules for effectiveness. Participants are randomised in a ratio of 1:1 to PCT-guided assessment added to NEWS2 and local standard care, or NEWS2 and local standard care alone. The participant flow diagram (Figure 1) provides further details.

Canolfan Ymchwil Treialon

[figure not shown]

Figure 1: PRONTO trial participant flow diagram.

TPL/008/2(v1.0)

Short title:

ISAP / SAP Template

Canolfan Ymchwil Treialon

Short title: ISAP / SAP Template

3.2 RANDOMISATION

Individual patients with suspected sepsis were randomised in a 1:1 ratio to either standard clinical management based on NEWS2 (control), or standard clinical management based on NEWS2 plus PCT-guided assessment (intervention). We used minimisation with NEWS2 score and site as stratification factors and added a random element to reduce the risk of subversion. This was implemented in a secure 24-hour web-based randomisation programme controlled centrally by the Centre for Trials Research.

The first patient was allocated at random. For each subsequent patient the software calculated the covariate sums as explained in Altman & Bland (2005) and determined which arm the patient should be allocated to in order to minimise the covariate imbalance. The patient was then randomised with an 80% chance of being allocated to the arm that minimised the imbalance (and a 20% chance of being allocated to the other arm). If neither arm minimised the imbalance because the covariate sums were equal for both arms (i.e., a state of perfect balance) the patient was allocated at random.

3.3 SAMPLE SIZE

The sample size calculation was based on two co-primary outcomes:

1. 28-day mortality, for which we want to show non-inferiority of the PCT-guided assessment as compared to current standard practice, using an absolute 2.5% non-inferiority margin. Assuming 28-day mortality of 15% in patients managed as suspected sepsis treated in the ED, any increase in 28-day mortality from 15% to not more than 17.5% would be considered non-inferior. For 90% power and one-sided 5% significance level, the sample size required is 7002, assuming there is no difference in 28-day mortality between arms. Our patient focus group were also consulted on the 2.5% non-inferiority margin and felt that this was acceptable if there were mechanisms to monitor trial outcomes, and if this was what was needed to provide a sample size which would ensure the trial could be completed as well as answer the research question.

2. Initiation of antibiotic treatment, for which we want to show superiority. Currently, around 90% of patients managed as suspected sepsis receive antibiotics (Royal Liverpool and Broadgreen University Hospitals NHS Trust, unpublished data). Reducing this by 10 percentage points to 80% would be seen as a success. To detect such an effect with 90% power and a two-sided 5% significance level, the sample size required is 532, which is substantially lower than what is needed for the non-inferiority endpoint. With 7002 patients, we would be able to detect effects as small as a reduction from 90% to 87.6% prescriptions with 90% power.

Accounting for 5% dropout, a fixed-sample design would need a total sample size of 7372.

We planned to conduct one interim analysis (after 50% of patients provided data) with options to stop the trial early using group-sequential boundaries based on O'Brien-Fleming type alpha spending (O'Brien & Fleming, 1979, DeMets & Lan, 1994). We used a hierarchical approach (Figure 2) to recommend stopping for effectiveness if:

TPL/008/2(v1.0)

Canolfan Ymchwil Treialon

Short title:	ISAP / SAP Template
--------------	---------------------

- the PCT-guided assessment was non-inferior in terms of 28-day mortality and superior in terms of initiation of antibiotics, or
- the PCT-guided assessment was superior in terms of 28-day mortality (i.e., a significant reduction to less than 15%).

The group-sequential design increased the total maximum sample size (in case the study was not stopped after the interim analysis) by just over 4% to 7676 (inflated for 5% dropout). The sample sizes were calculated using PROC POWER and PROC SEQDESIGN in SAS version 9.4 (SAS Institute Inc., Cary, NC, USA).

[figure not shown]

Figure 2: Overview of decision-making at the interim analysis of the co-primary outcomes.

3.4 FRAMEWORK

The effect of 28-day mortality will be investigated for non-inferiority of the PCT-guided assessment as compared to current standard practice, using an absolute 2.5% non-inferiority margin. For measuring the effect of initiation of antibiotics treatment, we want to show superiority.

3.5 INTERIM ANALYSES

TPL/008/2(v1.0)

Canolfan Ymchwil Treialon

Short title:	ISAP / SAP Template

A planned interim analysis was conducted after 43% (3040/7002) of participants had been recruited and followed up for 28 days. A second, unplanned interim analysis was requested by the Independent Data Monitoring Committee (IDMC) and conducted after 57% (3973/7002) of participants had been recruited and followed up for 28 days.

A full description of the interim analysis strategy and stopping rules is provided in the interim SAP.

3.5.1 PLANNED SAMPLE SIZE ADJUSTMENT

Not applicable.

3.6 TIMING OF FINAL ANALYSIS

Data collection will be completed by November 2023. Data cleaning will take place between November 2023 and March 2024. Data analysis will take place between April and July 2024 and be published in the autumn of 2024.

TPL/008/2(v1.0)

Canolfan Ymchwil Treialon

Short title:	ISAP / SAP Template

3.7 TIMING OF OUTCOME ASSESSMENT

Outcome data will be recorded daily by the research nurse for all recruited participants (up to and including day 28, or until discharge). Patient reported outcome data (health-related quality of life and resource use questionnaires) will be recorded at day 28 and day 90, with the exception of those recruited within the last 3 months of the study (to maximise recruitment, we stopped collecting these questionnaires on the 29/04/22 so they have not been collected for all participants). Research nurses will review observation and medication charts, and medical notes for all recruited participants to collect the data described in Table 2 below:

Table 2: Outcome data collection

Outcome	Data source	Type of data	Frequency	By whom
Antibiotic (Abx) initiation	Observation (Obs) charts/medical notes/drug charts	Time of initiation, Abx type, dose, duration	Admission/daily	Research Nurse
Abx use (IV and oral) in-patient	Obs charts/medical notes/drug charts	Abx type, dose, duration	Daily	Research Nurse
Abx use (IV and oral) post discharge up to 28 days	Obs charts/medical notes/drug charts/patient report/GP record	Abx type, dose, duration	Up to 28 days	Research Nurse
Adverse events	Obs charts/medical notes	Date, type	Daily	Research Nurse
Intensive care unit (ICU) usage	Medical notes	Date, details of admission/discharge to ICU	Daily	Research Nurse
COVID diagnosis	Medical notes	Date, clinical or laboratory confirmed	Up to 28 days	Research Nurse
Unscheduled readmissions	Medical notes	ICU readmissions, readmissions post discharge	Daily	Research Nurse
Mortality	Medical notes	Date, description	Up to 90 days	Research Nurse
Discharge	Medical notes	Date, description	Up to 90 days	Research Nurse

Canolfan Ymchwil Treialon

Serious adverse drug reactions (ADRs)	Medical notes	ADR(s)	Daily	Research Nurse
Health utility	Patient reported	-	Day 28 and day 90	EQ-5D/5L, patient reported questionnaire, collected by telephone or by post
Health-related quality of life (EQ- 5D/5L)	Patient reported	-	Day 28 and day 90	Patient reported, collected by telephone, or by post
Resource use	Patient reported	Direct medical costs and resource use	Day 28 and day 90	Patient reported, collected by telephone, or by post

4. STATISTICAL PRINCIPLES

4.1 LEVELS OF CONFIDENCE AND P-VALUES

ISAP / SAP Template

Short title:

The trial follows the group-sequential approach with one interim analysis; thus, p-values will be adjusted using the O'Brien-Fleming type alpha spending approach. For the hypothesis testing, any p-value less than the adjusted level of significance at the final analysis (Table 1 in Section 3.5.2) will be considered sufficient evidence to reject the hypothesis.

We will consider the 95% confidence limit (corresponding to a 5% significance level) as a benchmark for all analyses. We will estimate a two-sided 90% confidence interval (corresponding to a 95% one-sided confidence level) to assess the non-inferiority of the 28-day mortality outcome, and a two-sided 95% confidence interval to assess the superiority of the IV antibiotic initiation outcome. We will report both unadjusted and OBF adjusted confidence intervals for both co-primary outcomes.

We will also report bias-adjusted confidence intervals for group sequential designs, calculated using Jennison and Turnbull's repeated CI approach (Jennison & Turnbull, 1989).

Results will be presented in line with the CONSORT statement and its extensions for non-inferiority (Piaggio et al., 2012) and adaptive designs (Dimairo et al., 2020).

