6.2.1.2 PRIMARY OUTCOME ANALYSIS

We will use complete case analysis for the co-primary outcomes, meaning that we will only include participants with valid responses to both co-primary outcomes in the primary analysis. We will fit separate two-level logistic regression models (patients nested within sites) to model both co-primary outcomes, controlling for baseline NEWS2 score (minimisation variable). Results will be reported as risk differences with corresponding confidence intervals (calculated via the delta method (Norton et al., 2013)); a two-sided 90% interval for 28-day mortality (OBF adjusted to 90.18%), and a two-sided

TPL/008/2(v1.0)

Canolfan Ymchwil Treialon

Short title: ISAP / SAP Template	
----------------------------------	--

95% interval for IV antibiotic initiation at 3 hours (OBF adjusted to 95.04%). Non-inferiority in 28-day mortality will be concluded if the upper bound of the confidence interval is below +2.5% on the risk difference scale.

The individual analyses for the co-primary outcomes and corresponding inferences are described in the table below:

128-day mortality228-day mortality	Non-inferiority test with a margin of 2.5% H ₀ : $p_2 - p_1 \ge 0.025$ Superiority test	O'Brien-Fleming alpha spending (one-sided alpha = 0.05) Reject null if P < 0.0491 Critical value = 1.654 O'Brien-Fleming alpha spending (one-sided alpha = 0.05)
= = = = = = = = = = = = = = = = = = = =	Superiority test	O'Brien-Eleming alpha spending (one-sided alpha = 0.05)
	$H_0: p_1 - p_2 \le 0$	Reject null if P < 0.0491 Critical value = 1.654
3 IV antibiotic initiation at 3 hour	H ₀ : $p_1 - p_2 \neq 0$	O'Brien-Fleming alpha spending (two-sided alpha = 0.05) Reject null if P < 0.0496 Critical value = 1.964 the control and intervention arm, respectively.

 Table 5: Inferences for analyses of co-primary outcomes

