7.4 OTHER SOPS OR GUIDANCE DOCUMENTS

Randomisation plan: P:\152310305\PRONTO\eTMF\8.0 Data Management\8.5 Statistics\ Randomisation

Interim SAP: P:\152310305\PRONTO\eTMF\8.0 Data Management\8.5 Statistics\Statistical Analysis Plan\Interim SAP

SAP DEVIATION LOG

Document number:	Document version:	
Reason for deviation:		

TPL/008/2(v1.0)

Canolfan Ymchwil Treialon

Deviations from the planned analyses:

- For the ED subgroup analysis, we have used the site's % of participants waiting greater than
 >12hours from decision to admit at the time of randomisation, rather than the tercile, to reflect the increasing ED crowding
- We have not calculated the MLE or UMVUE estimates described in section 6.2.1.2 as the IDMC decided to continue the trial after the interim analysis even though the trial could have stopped according to the stopping criteria described in section 3.5.2

The following post-hoc exploratory analyses have been conducted on the following dates to understand the mechanism behind the results:

24/06/24:

- Descriptive tabulation of antibiotics and broad-spectrum antibiotics by arm
- Descriptive tabulation of ventilation and vasopressor by arm
- Descriptive tabulation of the participant timeline/pathway by arm
- Descriptive tabulation of the co-primary outcomes (28-day mortality and IV abx within 3-hours) by arm and NEWS2 score
- Descriptive tabulation of the algorithm risk vs clinical risk assessment by arm and NEWS2

11/07/24:

- Breakdown of amoxicillin and co-amoxiclav by IV/oral in the descriptive table of antibiotics by arm
- Descriptive tabulation of non-antibiotics (e.g., antivirals, anti-parasitic etc.) prescribed by arm
- Descriptive tabulation of the 10 most frequent combinations of first 2 abx prescribed simultaneously
- Descriptive summary (median [IQR]) of the number of days on broad-spectrum abx per participant per arm
- Descriptive tabulation of the proportion of participants who received two narrow spectrum abx simultaneously as their first abx
- Descriptive tabulation of 28-day mortality by algorithm risk category by arm
- Descriptive summary of the mean days on any abx by algorithm risk category by arm
- Explore whether mortality (adjusted for NEWS2) differed by site using post estimation of random effects

15/08/24:

- Descriptive tabulation of the first prescription given by arm
- Post-hoc subgroup analysis (using same methods described in section 6.2.6) of time to IV (secondary outcome #1) by NEWS2

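### The final critical values and interval levels allow for one interim look, but the SAP reports two and gives the second, at 57%, neither a boundary nor alpha

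*SAP*

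**What the plan says.** Section 3.3 sets out the design: "We planned to conduct one interim analysis (after 50% of patients provided data) with options to stop the trial early", with O'Brien-Fleming type alpha spending. Section 3.5 reports what happened. First, "A planned interim analysis was conducted after 43% (3040/7002) of participants had been recruited and followed up for 28 days". A further look is then recorded in the same place: "A second, unplanned interim analysis was requested by the Independent Data Monitoring Committee (IDMC) and conducted after 57% (3973/7002) of participants".

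Section 3.5.2 explains that the boundaries were re-estimated because the first look fell at 43% and not at 50%. Table 1 has columns for information 0.430 and 1.000 only. It gives final critical values of 1.654 (Tests 1 and 2, one-sided p 0.0491) and 1.964 (Test 3, two-sided p 0.0496), each with cumulative alpha of 0.0500.

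Section 4.1 still states "The trial follows the group-sequential approach with one interim analysis" and takes the adjusted significance levels from Table 1. Table 5 repeats the values. Section 6.2.1.2 turns them into a 90.18% interval for mortality and a 95.04% interval for antibiotic initiation. The stopping rules are left to an interim SAP.

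**The concern.** Sections 3.5 and 4.1 disagree on the number of interim analyses, and the decision thresholds follow the lower count. A spending function can absorb an unplanned look, but only if the alpha for that look is charged and the final boundary is recalculated. The SAP did this when the first look moved from 50% to 43%. It did not do it for the look at 57%, and it does not explain why it was unnecessary.

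The interval level is itself the decision rule here, because non-inferiority is concluded when the upper limit lies below +2.5%. The thresholds for all three tests are affected. So is the cumulative alpha of 0.0500 in Table 1, which a reader cannot verify without knowing what was done at 57%. Section 4.1 also promises Jennison-Turnbull repeated confidence intervals, which need a critical value for every look at which effectiveness was assessed. The SAP does not say which looks or boundaries enter them.

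**Working it through.** **Inputs.** First look: information 0.430 (Table 1; 3040/7002 = 0.434). Second look: 3973/7002 = 0.567 (section 3.5). Alpha: 0.05 one-sided for Tests 1 and 2, 0.05 two-sided for Test 3 (Table 5). Spending: O'Brien-Fleming type (section 3.3), taken in the Lan-DeMets form α(t) = 2[1 − Φ(z(1−α/2)/√t)], with α = 0.025 per side for Test 3. Crossing probabilities come from recursive numerical integration of the joint normal distribution, with correlation √(t1/t2) between looks.

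**Step 1: reproduce Table 1 with looks at 0.43 and 1.**
- Tests 1 and 2: 1.960/√0.43 = 2.989, so alpha spent is 2[1 − Φ(2.989)] = 0.0028 and the interim boundary is 2.770. The final value c solves P(Z1 < 2.770, Z2 ≥ c) = 0.0500 − 0.0028 = 0.0472. This gives c = 1.654, p = 0.0491, and an interval level of 1 − 2 × 0.0491 = 90.18%.
- Test 3: 2.241/√0.43 = 3.418, so alpha spent over both sides is 2 × 2[1 − Φ(3.418)] = 0.0013 and the interim boundary is 3.225. The final value is 1.964, p = 0.0496, and the level is 1 − 0.0496 = 95.04%.

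Every boundary and significance level in Table 1 is matched, so the stated values contain nothing for the second look.

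**Step 2: the same function with looks at 0.43, 0.567 and 1.**

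| | Cumulative alpha | Boundaries | Final p | Interval level |
|---|---|---|---|---|
| Tests 1 and 2 | 0.0028 / 0.0093 / 0.0500 | 2.770 / 2.391 / 1.675 | 0.0470 (one-sided) | 90.6% |
| Test 3 | 0.0013 / 0.0059 / 0.0500 | 3.225 / 2.779 / 1.977 | 0.0481 (two-sided) | 95.19% |

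**Step 3: total error if 1.654 and 1.964 are kept.** This depends on what could have happened at 57%, which the SAP does not state.

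| Assumed rule at 57% | Tests 1 and 2 (one-sided) | Test 3 (two-sided) |
|---|---|---|
| Spending-function boundary (2.391; 2.779) | 5.19% | 5.14% |
| First-look boundary reused (2.770; 3.225) | 5.03% | 5.01% |
| No effectiveness test | 5.00% | 5.00% |

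For the first row, the probabilities by look are 0.00280 + 0.00647 + 0.04268 for Tests 1 and 2, and 0.00126 + 0.00459 + 0.04557 for Test 3.

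**Step 4: effect on the limits at the planned size (7002, so 3501 per arm).**
- Mortality, 15% in both arms: SE = √(2 × 0.15 × 0.85/3501) = 0.853 percentage points. The shift is (1.675 − 1.654) × 0.853 = 0.018 points.
- Antibiotics, 90% against 80%: SE = √((0.09 + 0.16)/3501) = 0.845 points. The shift is (1.977 − 1.964) × 0.845 = 0.011 points.

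**The case against.** The strongest reply is that the SAP never says the 57% analysis tested effectiveness. A reader might infer that it did, and so that the final tests spend more than 5%. The only stopping rules the SAP describes are for effectiveness, and the deviation log records that "the IDMC decided to continue the trial after the interim analysis even though the trial could have stopped according to the stopping criteria". But that entry speaks of one interim analysis without saying which, and the rules themselves are in a document that is not shown. The inference is plausible but not established. If effectiveness was not tested at 57%, the stated thresholds are correct. If success could be claimed only at the final analysis, the final tests alone spend 4.91% and 4.95%.

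A reader might also reach error rates of 7% to 8% by supposing that the final cut-offs were applied at 57% (7.65% and 8.01%). Nothing in the SAP supports such a rule; its only interim boundaries are 2.770 and 3.225.

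It is also fair to say that the figures in Step 3 are per test. Stopping on non-inferiority also required antibiotic superiority, so crossing Test 1 or Test 3 alone did not stop the trial, although Test 2 alone could.

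Nor is the choice of 7002 as denominator a source of leniency. The group-sequential maximum less dropout, 7676 × 0.95 = 7292, gives fractions of 0.417 and 0.545 and final values of 1.670 and 1.974, slightly less strict than 1.675 and 1.977.

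What remains is that sections 3.5 and 4.1 contradict each other, and the SAP gives no reason for leaving the second look out of the error accounting.

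**Conclusion.** The point holds as an omission with a small, conditional effect. The final thresholds are those of a design with a single interim look, while two were taken. Whether total error exceeds 5% depends on whether the 57% analysis could have led to a stop for effectiveness. If it could, under the trial's own spending function, the excess is about 0.19 percentage points for each mortality test and 0.14 for the antibiotic test. If the first-look boundary was reused, it is about 0.03 points or less. If effectiveness was not tested, it is nil.

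The SAP does not support a flat statement that the final tests exceed 5%, or that the repeated confidence intervals under-cover. The results assume the Lan-DeMets form (which reproduces Table 1) and 7002 as the denominator. A shift of about 0.02 points against a 2.5-point margin would matter only for a result very close to the margin. This should be fixed, but it does not threaten the trial.

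**What to change.** In section 4.1, change one interim analysis to two. In section 3.5 or 3.5.2, state which of Tests 1 to 3 were run at 57%, against what boundary, and whether stopping for effectiveness was possible.

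If it is documented that no such stop was possible, say so and justify that no alpha was spent; the stated thresholds can then stay. Otherwise, recompute the boundaries for all three looks. Use about z = 1.675 (one-sided p < 0.0470, 90.6% interval) for Tests 1 and 2, and about z = 1.977 (two-sided p < 0.0481, 95.2% interval) for Test 3. Carry these into Table 1, Table 5, sections 4.1 and 6.2.1.2, and the critical values for the repeated confidence intervals. Record the change in the deviation log, which shows that analyses have already been run.

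The cost is some wording, one boundary calculation and slightly stricter thresholds. No further patients are needed.
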